### 2.2 Interleukin 2 (Aldesleukin)

The Cytokine Working Group performed a phase III trial in which patients were randomized to

NCI Protocol #: 7870

receive either outpatient aldesleukin (5 MIU/m^2 subcutaneously every 8 hours x 3 doses on day 1 then daily 5 days/week for 4 weeks) and IFN $\alpha$  (5 MIU/m^2 subcutaneously thrice weekly for 4 weeks) every 6 weeks or standard high dose inpatient aldesleukin (600,000 IU/kg/dose every 8 hours intravenously, days 1-5 and 15-19 [max 28 doses]) every 12 weeks. The response rate for high-dose aldesleukin was 23% (22/95) versus 10% (9/91) for aldesleukin / IFN $\alpha$  (p=0.018). Eight patients achieved a complete response on high dose aldesleukin versus only 3 on low dose aldesleukin / IFN $\alpha$ . The median response durations were 24 months for high dose aldesleukin and 15 months for aldesleukin / IFN $\alpha$  (p=0.18). Median overall survivals were 17 and 13 months (p=0.21), favoring high dose aldesleukin. Ten patients on high dose aldesleukin were progression free at 3 years versus 3 on aldesleukin / IFN $\alpha$  (p=0.08). Durable CRs favored HD aldesleukin (7 vs. 0). Median progression free survival was 3 months for each treatment arm. Another three-arm randomized study compared response rates and overall survival for patients with metastatic RCC receiving high-dose or one of two low-dose aldesleukin regimens. Major tumor regressions, as well as complete responses, were seen with all regimens tested but high dose aldesleukin was more clinically active, although this did not produce an overall survival benefit. Taken together these data suggests that high dose aldesleukin should remain the preferred therapy for appropriately selected patients with access to such therapy before or after the use of the recently FDA approved receptor tyrosine kinase inhibitors sorafenib and sunitinib. However, given the toxicity and limited efficacy of high dose aldesleukin therapy, additional efforts should be directed to increase the efficacy of immunotherapy.

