#### Secondary Objectives:

Secondary endpoints will be used to determine the effect of entinostat on progression free survival (PFS), survival, time-to tumor progression and parameters measuring immune response.

Failure rates will be used to compare the PFS, overall survival and time-to-tumor progression of metastatic RCC patients treated with high dose aldesleukin combined with entinostat to the historical failure rates of patients treated with high dose aldesleukin alone. The failure rate is estimated by dividing the number of events ( $d$ ) by the sum of the exposure time in the study

cohort:  $\lambda = d / \sum t_i$ . The 95% confidence interval is calculated as:  $\lambda \pm Z_{1-\alpha/2} \frac{\lambda}{\sqrt{d}}$ .

The historical PFS failure rate observed in the randomized trial of IL-2 reported by the Cytokine Working Group was 2.77 per person year (median PFS of 3 months). Patients eligible for this study are expected to be homogenous group with comparable prognostic characteristics. Enrollment is expected to be between 1 and 2 patients per month with an accrual period of 6 years and 12 months of follow-up. With a total of 34 events in 36 patients, the study would yield 79% power to detect a decrease in the PFS failure rate to 1.85 per person year of follow-up (an increase of 1.5 months in the median PFS compared to the historical median) at an alpha level of 0.1 (one-sided).

We do not expect that different doses of entinostat during the period off aldesleukin (maintenance) will affect the primary endpoint since objective responses have been rarely observed with single agent entinostat. We expect that the vast majority of patients will be able to tolerate the 10 mg maintenance dose if the phase II recommended dose in combination with aldesleukin is 5 mg. Should we observe discrepancies in the maintenance dose level of entinostat we will consider subgroup analysis to determine the secondary objective PFS in the different group of patients.

The toxicity of IL-2 when combined with entinostat will be further characterized following the phase II portion of this study. The exact binomial proportion for prolonged grade 4 toxicities with the 95% confidence interval will be given. Additional toxicity frequencies, proportions, and 95% CIs will be given by type and grade of toxicity.

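### The historical PFS rate of 2.77 per person-year is a 3-month median converted under a constant hazard; comparing events per person-time with it can credit IL-2's own long-term progression-free patients to entinostat

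*Combined protocol and SAP*

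**What the plan says.** Section 11.3 (Secondary Objectives) compares PFS, overall survival and time to progression with historical high-dose aldesleukin by means of failure rates. "The failure rate is estimated by dividing the number of events" by total exposure time, with a two-sided 95% interval of the rate plus or minus z times rate/√d, where d is the number of events.

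For PFS the benchmark is described as "The historical PFS failure rate observed in the randomized trial of IL-2 reported by the Cytokine Working Group", with the value 2.77 per person-year and a 3-month median in parentheses. No event count or person-time is given for it. The power statement is 79% to detect a fall to 1.85 with 34 events in 36 patients at one-sided alpha 0.1, "with an accrual period of 6 years and 12 months of follow-up".

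Section 2.2 describes the same high-dose arm: "Median progression free survival was 3 months for each treatment arm"; "Ten patients on high dose aldesleukin were progression free at 3 years versus 3 on aldesleukin"/IFNα; "The response rate for high-dose aldesleukin was 23% (22/95"); "The median response durations were 24 months for high dose aldesleukin"; and "Eight patients achieved a complete response on high dose aldesleukin".

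On follow-up, section 4.1 stops entinostat eight weeks after a documented complete response. Footnote 4 of the study calendar ties later scans to being on entinostat, while section 9 gives the same interval without that condition. Section 4.3 provides only survival contact after therapy, until the primary endpoint is complete or the study ends. No PFS censoring rule is given.

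**The concern.** Events over person-time summarises PFS in a single number only if the hazard is constant. High-dose IL-2 is known for early progression in most patients and very long control in a few, and section 2.2 reports exactly that. Those few add person-time and almost no events. The estimated rate therefore depends on how long they are followed, and it can fall below 2.77 with no contribution from entinostat.

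Section 1.3.1 makes the comparison with aldesleukin alone a stated objective, so a rate below 2.77 could be reported as a PFS gain over historical IL-2. The stated power rests on the same constant-hazard assumption.

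**Working it through.** **1. Origin of 2.77 and 1.85.** ln 2 / 0.25 y = 2.773, and ln 2 / 0.375 y = 1.848. Both are medians (3 and 4.5 months) converted under a constant hazard.

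**2. The plan's 79%.** Expected events at 2.77 with 12 months per patient: 36 × (1 − e^−2.773) = 33.75, close to the stated 34. With person-time fixed so that 34 events are expected at 2.77, an exact Poisson test rejects at 26 or fewer: size 0.095, power at 1.85 of 0.791. The normal form agrees: Φ[((1 − 2/3)√34 − 1.2816)/√(2/3)] = 0.791. So 79% is arithmetically right under a constant hazard.

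**3. Does section 2.2 fit a constant 2.77?** The PFS denominator is not stated; 95 is taken from the response rate.
- At 3 years: 95 × e^(−3 × 2.773) = 0.02 predicted, against ten reported. The exact 95% CI for 10/95 is 5.2% to 18.5%. It would take 10/e^−8.318, about 41,000 patients, for 2.77 to predict ten.
- At 24 months: 22 responders with a 24-month median duration leave about 11 still in response 24 months after onset. The constant hazard predicts 95 × e^(−2 × 2.773) = 0.4 progression free.

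**4. Effect on events/person-time under IL-2 alone.** Take a cure mixture through 50% at 3 months and 10/95 = 0.105 at 3 years. The hazard in the other patients is −ln[(0.5 − 0.105)/(1 − 0.105)]/0.25 = 3.273.
- 12 months per patient: events 0.895 × (1 − e^−3.273) = 0.861; person-time 0.105 + 0.861/3.273 = 0.368; rate 2.34.
- 6-year accrual plus 12 months (mean follow-up 4 years): 0.895/(4 × 0.105 + 0.895/3.273) = 1.29.

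**5. False positives with no entinostat effect.** 36 patients, 40,000 simulated trials per cell, log-rate test at one-sided 0.10 (our choice, because the plan names none). The plateau curve has hazard 2.773 until survival reaches 10/95, then is flat. The response-based curve has 22/95 responders with PFS = 0.25 y + response duration (median 2 y, exponential or Weibull shape 0.5) and the others at 4.21 per year, so that the median is 3 months. It predicts 8.5 or 9.8 of 95 progression free at 3 years, close to the ten reported.

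| IL-2-alone curve | 12 months each | 18-month accrual + 12 | 36-month accrual + 12 | 6-year accrual + 12 |
|---|---|---|---|---|
| Constant hazard (control) | 0.09 | 0.09 | 0.08 | 0.08 |
| Plateau | 0.18 | 0.54 | 0.73 | 0.86 |
| Cure mixture | 0.37 | 0.67 | 0.81 | 0.91 |
| Response-based | 0.43–0.58 | 0.74–0.84 | 0.85–0.90 | 0.91–0.93 |

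At the stated 1 to 2 patients per month, 36 patients take 36/2 = 18 to 36/1 = 36 months, hence the middle columns. With shorter windows the mixture gives 0.08 at 3 months, 0.14 at 6 and 0.24 at 9.

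**6. Using the plan's own 95% interval.** The upper limit falls below 2.77 (nominal 2.5%) in 3% to 4% of control trials. On the other curves it does so in 9% to 46% at 12 months and 83% to 90% with 6-year accrual.

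**7. Sensitivity.**
- *Partial early censoring at about 5 months (assumed).* With 70% of tail patients censored: plateau 0.03 and mixture 0.15 at 12 months; 0.42 and 0.51 with 6-year accrual. With the longest 8 of 22 responses censored on the response-based curve: 0.18–0.34 and 0.43–0.54.
- *Full early censoring.* With every tail patient censored then, the plateau gives 0.003 and the mixture 0.06–0.07 in every window.
- *Lower confidence limits, 12 months.* With 3-year PFS at 5.2%: plateau 0.08, mixture 0.20. With the response rate at 15.1%: 0.27–0.38.
- *Weibull through the same two points.* It gives 0.81 at 12 months but puts 34% of progressions in the first month, so it is not relied on.
- *Shape-free bound.* At most 85 events; ten patients contribute 3 years each and at least 37 others contribute 0.25 years. With complete 3-year follow-up the rate is at most 85/(30 + 9.25) = 2.17. With 12 months it is at most 85/(10 + 9.25), about 4.4, which does not exclude 2.77.

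**The case against.** The plan names no PFS test. It gives an estimator and a 95% interval, and the 10% alpha appears only in the power sentence. The 3-month median is printed next to 2.77, so the derivation is half disclosed, and exponential power is an ordinary planning statement. The 34 events fit 12 months per patient, so the window is ambiguous rather than absent. The largest error rates need the 6-year reading, with progression-free patients scanned for up to seven years. On the 12-month reading the size is not identified: it runs from conservative to above 50% depending on curve shape and censoring, and neither the shape nor the PFS denominator is in the documents. PFS is secondary, and activity is judged on response.

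Much of this stands as a limit on size. The 12-month figures should lead, and they are conditional on shape and censoring. It does not rescue the comparison. The plan's own interval fails in the same way, so the missing test is no defence. At 12 months with no early censoring, every curve passing through section 2.2's reported values exceeds the nominal level. The conservative cases require a censoring rule the plan does not state.

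**Conclusion.** The concern holds. The figure 2.77 is a converted median, not an observed rate, and section 2.2 contradicts the constant hazard behind it. With no entinostat effect, the false-positive rate at nominal 10% is about 18% to 58% with 12 months per patient and 86% to 93% with 6-year accrual plus 12 months. It stays near or below 10% only if PFS follow-up is short, or tail patients are censored early, or the true tail is at the low end of its confidence interval on one curve shape.

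These figures assume 95 as the PFS denominator, the listed curve shapes and a log-rate test. The direction is well supported; the exact size is not. The 79% power is correct only under a constant hazard. The method should be corrected, but the primary response analysis is unaffected.

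**What to change.** 1. Describe 2.77 as derived from the 3-month median under a constant hazard.
2. Replace the comparison of events/person-time with 2.77 by Kaplan-Meier PFS, with 95% confidence intervals for the median and fixed landmarks, set descriptively beside the historical 3-month median and the ten patients at 3 years. If the published high-dose IL-2 PFS curve can be obtained, a one-sample log-rank test against it is an alternative.
3. State one PFS follow-up window and one censoring rule. This requires saying whether the 12 months is per patient or after the last entry, reconciling the 6-year accrual with 18 to 36 months at the stated enrolment rate, and reconciling calendar footnote 4 with section 9 on scans after entinostat stops.
4. Withdraw the 79%, or restate it as conditional on a constant hazard or for the new test.

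The cost is wording and one recalculation. The statistical change itself adds no patients or procedures; whether reconciling the scan passages does is for the sponsor to settle. Without the published curve, the formal PFS test and its power statement are given up. With it, little is lost: taking the response-based curve as an exactly correct reference, the one-sample log-rank test had size 0.08–0.09 and power 0.78–0.83 for a hazard ratio of 0.667. That ignores sampling error in the historical arm.

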## 3. PATIENT SELECTION

### 3.1 Eligibility Criteria

- 3.1.1 Patients must have pathological diagnosis of renal cell carcinoma that is metastatic or surgically unresectable. The histology must be clear cell carcinoma or predominant clear cell carcinoma.
- 3.1.2 Patients may have received up to two prior therapies including VEGF, mTOR and PD-1/PDL1 inhibitors. Prior palliative radiation to metastatic lesion(s) is permitted, provided there is at least one measurable and/or evaluable lesion(s) that has not been irradiated.
- 3.1.3 Patients must have measurable or evaluable disease.

- 3.1.4 Age  $\geq$  18 years.
- 3.1.5 ECOG performance status 0 (see Appendix B).
- 3.1.6 Life expectancy of greater than 6 months.
- 3.1.7 Patients must have normal organ and marrow function as defined below:
- Hemoglobin  $\geq$ 12 g/dL
  - Leukocytes  $\geq$ 3,000/mm^3
  - Absolute neutrophil count  $\geq$ 1,500/mm^3
  - Platelets  $\geq$ 100,000/mm^3
  - Total bilirubin  $\leq$ 1.5 x laboratory upper limit of normal
  - AST(SGOT)/ALT(SGPT)  $\leq$ 2.5 x laboratory upper limit of normal
  - Creatinine  $\leq$ 1.5 x laboratory upper limit of normal or Calculated Creatinine clearance of  $\geq$ 50ml/min (please use institutional formula)
  - LDH WNL
  - Corrected calcium  $\leq$ 10 mg/dL
  - PT/INR  $\leq$ 1.5
  - Urine protein  $<$ 1+; if  $\geq$ 1+, 24 hour urine protein should be obtained and should be  $<$ 1000 mg
- 3.1.8 Pulmonary: FEV1  $\geq$ 2.0 liters or  $\geq$ 75% of predicted for height and age. (PFTs are required for patients over 50 or with significant pulmonary or smoking history).
- 3.1.9 Cardiac: No evidence of congestive heart failure, symptoms of coronary artery disease, myocardial infarction less than 6 months prior to entry, serious cardiac arrhythmias, or unstable angina. Patients who are over 40 or have had previous myocardial infarction greater than 6 months prior to entry will be required to have a negative or low probability cardiac stress test for cardiac ischemia.
- 3.1.10 CNS: No history of cerebrovascular accident or transient ischemic attacks.

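### The historical PFS, OS and time-to-progression comparison rests on an unverified assumption of comparable patients, while entry allows zero to two prior therapies and no analysis looks at prior therapy

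*Combined protocol and SAP*

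**What the plan says.** Objective 1.3.1 and section 11.3 (Phase II, Secondary Objectives) compare time to progression, PFS and overall survival with historical results for aldesleukin alone. The method is a failure rate, events divided by total exposure, set against a fixed historical value. Section 11.3 states that value for PFS only: the historical rate "was 2.77 per person year (median PFS of 3 months"). The planned size is given as "With a total of 34 events in 36 patients", with the claim that "the study would yield 79% power to detect a decrease in the PFS failure rate to 1.85 per person year of follow-up", "at an alpha level of 0.1 (one-sided"), over "an accrual period of 6 years and 12 months of follow-up".

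Comparability with the historical patients is covered by one sentence: "Patients eligible for this study are expected to be homogenous group with comparable prognostic characteristics". No data, matching, adjustment or check accompanies it.

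On entry, section 3.1.2 says "Patients may have received up to two prior therapies including VEGF, mTOR and PD-1/PDL1 inhibitors", and 3.2.1 excludes only patients with more than two. Section 4.1, by contrast, describes eligible patients as having had no prior therapies. Section 2.2, reviewing the completed historical trial, regards aldesleukin as a suitable choice "before or after the use of the recently FDA approved receptor tyrosine kinase inhibitors sorafenib and sunitinib".

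**The concern.** There is no concurrent control, so the whole comparison depends on 2.77 per person-year being the rate the enrolled patients would have had on aldesleukin alone. If patients range from untreated to twice treated, that rate depends on the mix and on how prior therapy affects PFS. The plan fixes neither and measures neither.

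The same PFS result could then come from an entinostat effect, from the prior-therapy mix, or from both. As written, the analysis cannot show which. A reader could be led to credit entinostat with a case-mix difference, or to miss a real effect that case mix has hidden.

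**Working it through.** **Inputs from section 11.3.** Historical rate 2.77 and target rate 1.85 per person-year, 34 events, 36 patients, one-sided alpha 0.10. Check of rates against medians: ln 2 × 12 / 2.77 = 3.00 months and ln 2 × 12 / 1.85 = 4.50 months. Rate ratio 1.85 / 2.77 = 0.668.

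**The plan's own power.** Take the exposure at which 34 events are expected at the historical rate: 34 / 2.77 = 12.27 person-years. At 1.85 the expected count is 1.85 × 12.27 = 22.7.
- Normal approximation to the Poisson: Φ((34 − 22.7 − 1.2816 × √34) / √22.7) = 0.789.
- Exact Poisson: reject at 26 events or fewer; alpha 0.095, power 0.791.

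The stated 79% reproduces, so the arithmetic is sound.

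**Test used below.** If the trial stops at the 34th event, total exposure at a common rate λ follows a gamma distribution with shape 34 and rate λ. The one-sided 0.10 test rejects when the observed rate is at or below 2.26 (median 3.68 months or longer). Power at 1.85 is 0.86. This differs from 79% only because the test differs, so the mixed-population power figures below should be read against 0.86.

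**A simple shift in the control median (assumed values).** The range shows the Poisson approximation, then the exact gamma test.

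| True aldesleukin-alone median | Gain declared, no entinostat effect | Power at rate ratio 0.668 |
|---|---|---|
| 2.5 months | 0.01 | 0.44 to 0.52 |
| 3.0 months | 0.10 | 0.79 to 0.86 |
| 3.5 months | 0.31 to 0.36 | 0.95 to 0.97 |

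A half-month error in the control median is enough to triple the false-positive rate or roughly halve power.

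**A prior-therapy mix (assumed values).** The documents give neither the pretreated share nor the effect of pretreatment on PFS. The ranges taken were a share of 25-75% and a pretreated-to-untreated hazard ratio of 0.7 to 1.5, with untreated patients at the historical rate. Each trial draws 36 exponential PFS times, stops at the 34th event and applies the gamma test; 100,000 trials per setting.

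| Setting, no entinostat effect | Trials declaring a gain |
|---|---|
| No mixing | 10% |
| 50% pretreated, hazard ratio 0.7 | 44% |
| 50% pretreated, hazard ratio 0.85 | 22% |
| 50% pretreated, hazard ratio 1.25 | about 3% |
| Whole range | 0.1% to 64% |

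If untreated patients on the combination have the target rate of 1.85, power over the same range runs from about 0.27 to 0.99, against 0.86 without mixing.

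**Search for a safeguard.** The baseline parameters that section 11.3 names for its logistic and Cox models are laboratory and immune markers; prior therapy is not among them. The only PFS subgroup mentioned is by maintenance dose of entinostat, and that is only to be considered. Nothing stratifies, adjusts or restricts the historical comparison by prior therapy.

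**What a stratum can deliver.** The gamma test of 1.85 against 2.77 has power of about 0.66 with 17 events and 0.47 with 8. By the plan's own interval formula, the half-width as a share of the rate is 1.96 / √d: 34% at 34 events, 48% at 17 and 69% at 8.

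**The case against.** **Tight entry criteria.** The sentence in 11.3 states only an expectation about prognosis, and section 3.1 does narrow prognosis: clear cell histology, ECOG 0, life expectancy over six months, normal LDH, hemoglobin of at least 12 g/dL and corrected calcium of at most 10 mg/dL. A reader might infer that the eligibility rules flatly contradict the sentence. They do not. Variable prior therapy leaves the expectation unsupported, and section 4.1 taken alone would fit it. But the same criteria may set these patients apart from the historical cohort, so they are a second possible source of difference rather than reassurance.

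**The historical cohort.** A reader might infer that it is known to be free of prior targeted therapy. The documents do not report its prior therapy. The wording in section 2.2 makes earlier VEGF-drug exposure unlikely; other prior systemic treatment is unknown. Comparing the untreated stratum with history is therefore not shown to be like for like.

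**Assumed magnitudes.** The shares and hazard ratios have no source in the documents. That objection stands: the range shows sensitivity and fixes neither the size nor the direction of bias.

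**Single-arm design.** Lack of a concurrent control is inherent in the chosen design, and stratifying does not cure it. That also stands, and it is a reason to call the comparison descriptive.

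**Conclusion.** The concern holds for the secondary comparison of PFS, overall survival and time to progression. The comparability sentence carries the comparison, nothing supports it, and sections 3.1.2 and 3.2.1 leave room for a mixed population that the analysis ignores. The 79% power is computed correctly, but it applies only if 2.77 is the right aldesleukin-alone rate for the patients enrolled.

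The size rests on assumption. With 25-75% pretreated, a hazard ratio of 0.7 to 1.5 and untreated patients at the historical rate, the nominal 10% false-gain rate becomes anything from 0.1% to 64%. The documents do not support a claim that the bias favours the combination, or that it disfavours it.

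A reader might also infer that the primary response test is compromised, because response rates of 40% in untreated and 20% in pretreated patients at an equal split give only a 0.53 chance of 11 or more responses in 36. That does not follow. The split implies a true overall rate of 30%, between the two hypotheses, and 0.53 is how the rule behaves at 30%. The rule uses fixed rates of 20% and 40%, not the historical failure rates or the comparability sentence.

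This should be corrected because it changes what the PFS comparison can support, but it does not threaten the primary decision.

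**What to change.** 1. Reconcile section 4.1 with 3.1.2 and 3.2.1 on prior therapy.
2. In 11.3, replace the comparability sentence with a statement that comparability with the historical cohort is an unverified assumption and that the PFS, overall survival and time-to-progression comparison is descriptive. Name prior therapy and the selective entry criteria as possible sources of difference.
3. Report the three failure rates with intervals separately for 0 and for 1-2 prior systemic therapies.
4. Pre-specify the untreated stratum against the historical rate as a sensitivity analysis beside the all-patient result, noting that it does not remove other differences from the historical cohort.
5. Leave the 11-of-36 response rule as it is.

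The cost is a few sentences and one table. The number of prior therapies is already needed to establish eligibility, so no new data are required, and sample size and treatment do not change. The drawback is the low precision in each stratum shown above, which is acceptable for a descriptive check.

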#### Dosing levels

Dose Level	Entinostat (mg, every 2 weeks, PO)	Aldesleukin (IU/kg, every 8hrs, IV)
0	1	600,000
1	3	600,000
2	5	600,000

Patients will receive only entinostat during the “maintenance” (between cycles) period. During Phase II, patients receiving 5 mg entinostat during the “maintenance” period will be given the option to dose escalate entinostat to 10 mg PO if tolerated except two weeks before and two weeks after administration of aldesleukin.

The recommended dose of 5 mg PO every 2 weeks was determined in the Phase I portion of the study. This cohort will be expanded in the phase II portion so that 36 new patients will be treated at this dose level. The evaluations for the phase II component of the study will be identical to the phase I portion.

Compliance will be assessed via patient diaries Also, pill containers will be returned to the study doctor or nurse at the end of each cycle.

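### The PFS subgroup by maintenance dose has no method that handles escalation after baseline, so a comparison by dose reached would favour 10 mg even with no dose effect

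*Combined protocol and SAP*

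**What the plan says.** Section 4.1 (Dosing levels) gives Phase II patients receiving 5 mg during maintenance the "option to dose escalate entinostat to 10 mg PO if tolerated except two weeks before and two weeks after administration of aldesleukin". Sections 4.1 and 4.2 keep patients on therapy only while they tolerate it and have not progressed.

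Section 11.3 (Phase II, Secondary Objectives) expects most patients to tolerate 10 mg. If maintenance doses turn out to differ, "we will consider subgroup analysis to determine the secondary objective PFS in the different group of patients". It does not define the groups, the PFS time zero, a landmark or a time-varying dose. The only rate estimator in that section is events over total exposure: "The failure rate is estimated by dividing the number of events" by the summed exposure time.

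Tumour assessment is at week 11 of each cycle, then every 8 to 12 weeks on entinostat (sections 8 and 9).

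**The concern.** Membership of the 10 mg group is decided after baseline and cannot be reached by anyone who has already progressed. If PFS is counted from treatment start and split by dose reached, the wait before escalation counts as event-free time for 10 mg, while patients who progress first stay in the 5 mg group. The 10 mg group then looks better with no drug effect behind it.

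For scale, the trial's own PFS target is a fall from 2.77 to 1.85 per person-year, a ratio of 1.85 / 2.77 = 0.67 and a median gain of 1.5 months. A bias of similar or larger size in a dose subgroup could be misread as a dose effect.

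**Working it through.** **Inputs from the documents.** Historical PFS rate 2.77 per person-year (median 3 months), 36 patients and the rate estimator are in section 11.3. Aldesleukin on days 1-5 and 15-19, and entinostat every 2 weeks from day -14, are in section 4.1. Scans are in sections 8 and 9.

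**The plan's own figure.** The plan states: "With a total of 34 events in 36 patients, the study would yield 79% power" for a "decrease in the PFS failure rate to 1.85 per person year of follow-up" at one-sided 0.10. If 34 is the number of events expected at the historical rate, exposure is 34 / 2.77 = 12.27 person-years, and 12.27 x 1.85 = 22.7 events are expected under the alternative. Rejecting at 26 or fewer events gives an exact Poisson alpha of 0.095 and power of 79.1%. The figure reproduces, so 2.77 is used below as the common rate with no dose effect.

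**When escalation can start.** Entinostat falls on days 1, 15, 29, 43, 57 and 71. Day 29 is within two weeks of the last aldesleukin day (19), so Day 43 is the first eligible dose in cycle 1. Day 57 also qualifies. Both precede the first scan, at about Day 77.

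**Closed form, progression observed continuously.** Let L be the common rate, t0 the escalation time and q the share of progression-free patients who escalate.

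- 10 mg rate = 1 / (t0 + 1/L)
- 5 mg rate = (1 - q e^(-L t0)) / (1/L - q e^(-L t0)(t0 + 1/L))

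With t0 = 6 weeks (0.115 years) and q = 0.5: e^(-L t0) = 0.727. The 10 mg rate is 1 / (0.115 + 0.361) = 2.10, the 5 mg rate is 0.636 / 0.188 = 3.39, and the ratio is 0.62. With t0 = 10 weeks and q = 0.8 the rates are 1.81 and 5.24, ratio 0.35.

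**Simulation, progression recorded only at scans.** Scans are at Days 77, 161 and 245, then every 70 days. Escalation chances fall at about Days 43, 127, 217 and 301, and PFS is counted from Day 1. In this setting only the inter-scan interval in which a patient escalates matters, not the exact day. Each scenario uses 400,000 patients. The false-positive rate is the share of 8,000 trials of 36 in which a two-sided 5% test of the log rate ratio favours 10 mg (nominal 2.5% in that direction). **All escalation probabilities are assumptions.**

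| Escalation | 10 mg rate | 5 mg rate | Ratio | False positive |
|---|---|---|---|---|
| Day 43 only (50-90%) | 2.08 | 2.08 | 1.00 | under 1% |
| 80% first, 20% later | 2.02 | 2.44 | 0.83 | about 1% |
| 80% first, 50% later | 1.98 | 3.20 | 0.62 | about 5% |
| 50% at each chance | 1.80 | 3.20 | 0.56 | about 30% |
| 80% at each chance | 1.98 | 4.13 | 0.48 | about 8% |
| 90% at each chance | 2.04 | 4.44 | 0.46 | under 1% |
| Cycle 2 or later, 50% | 1.31 | 3.19 | 0.41 | about 84% |
| Cycle 2 or later, 80% | 1.39 | 4.13 | 0.34 | about 99% |

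In the 50% row the medians are 5.3 and 2.5 months, a 2.8-month gap from no effect. Escalation only at Day 43 gives 1.00 because no progression has yet been recorded, so nobody has been excluded. The false-positive rate is low at high uptake because the 5 mg group is tiny: about 5% of 36, or 2 patients, at 90%.

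If 25% of progressions are found clinically between scans, the Day 43-only case (80%) falls from 1.00 to 0.76 and the 50% case from 0.56 to about 0.47.

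**Do the remedies work?** A Day 77 landmark gives 0.99 to 1.00 wherever both groups exist. With time-dependent dose (50% case), the chance of progression at each scan is the same for 10 mg and 5 mg patients at risk: 0.441 and 0.442 at Day 77, 0.469 and 0.469 at Day 161. Splitting person-time at escalation and using the constant-rate estimator does not work: with escalation before the first scan and scan-only detection it gives ratios of 1.7 to 6.5, because no event can be recorded before that scan.

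**The case against.** The strongest reply is that the plan does not commit to the biased analysis. It says only that a subgroup analysis will be considered, and only if doses differ. It names no 5 mg versus 10 mg test, no rate ratio and no grouping by dose reached. A reader might infer that a naive comparison is planned; the documents do not say so. What remains is that the one sentence given, combined with the only rate estimator in the section, leads to the biased comparison and nothing rules it out.

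A reader might also infer that the plan carries a bias of known size. It does not. No escalation share is given, and the expectation that most patients will tolerate 10 mg concerns tolerance, not uptake. With scan-only detection the bias disappears if everyone who escalates does so before week 11. Section 4.1 does not restrict escalation in that way: it is open during maintenance between cycles, and entinostat continues until progression or 8 weeks after a documented complete response.

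Third, the remedy does not rescue the comparison. Tolerance still selects the 10 mg group, and the 5 mg group may be a handful of patients. That is right, and it is why the analysis should be labelled descriptive.

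**Conclusion.** The gap is real: a PFS comparison by maintenance dose reached, counted from treatment start, would tend to favour 10 mg with no dose effect, and section 11.3 has no safeguard. The size is a matter of assumption. At 2.77 per person-year with exponential PFS and scan-only detection, the ratio runs from 1.00 (all escalation at about Day 43), through 0.46 to 0.83 (some first escalate after week 11), to 0.34 to 0.41 (escalation from cycle 2 only). Clinical detection between scans makes it more extreme. The false-positive rate ranges from under 1% to over 85%, so no single figure describes the plan.

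The affected analysis is conditional and secondary. The response-rate endpoint, its sample size and the whole-cohort PFS comparison with historical data do not depend on it. Nothing in the documents says the subgroup would be used to choose a dose.

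**What to change.** Replace the subgroup sentence in section 11.3 with: *Any comparison of PFS by maintenance dose will use dose as a time-dependent covariate in a Cox model, with a landmark analysis at the week 11 scan (dose reached by then, PFS counted from the landmark) as a sensitivity analysis if both groups exist at that time; it is descriptive and is not evidence of a dose effect, because tolerance selects the group.*

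State also how the covariate is coded around aldesleukin, when section 4.1 excludes 10 mg. The Cox model comes first because the landmark has no 10 mg group if escalation starts only in cycle 2.

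The cost is slightly more analysis work. The landmark drops those who progress by Day 77: at the historical rate 1 - exp(-2.77 x 77 / 365.25) = 44%, leaving about 20 of 36, possibly with few at 5 mg. No dose, schedule or sample size changes.
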